### **Change in EQ-5D from baseline**

The EQ-5D is among the key PRO variables of interest. EQ-5D profiles for each of the five dimensions (mobility, self-care, usual activities, pain/discomfort, anxiety/depression) will be tabulated by each level (no problems, slight problems, moderate problems, severe problems, and extreme problems) at baseline and each scheduled assessment.

EQ visual analogue scale (VAS) values will be summarized descriptively by arm for each scheduled visit.

The EQ VAS self-rating records of the respondent's own assessment on their health status. The EQ VAS scores are anchored on 100=the best health you can imagine and 0=worst health you can imagine.

Imputation: There should be only ONE response for each dimension. Missing values will be coded as '9'. Ambiguous values (e.g. 2 boxes are ticked for a single dimension) will be treated as missing values.

### **2.13 Bone marrow biopsy and aspirate**

The bone marrow biopsy and aspirate assessments data collected at baseline and end of treatment (if available) will be presented in listing. The bone marrow fibrosis is graded according to the IWG consensus criteria for treatment response (Tefferi 2013) and bone marrow blast count in percentage is measured for leukemic transformation.

## 2.15 Interim analysis

Not applicable.

## 3 Sample size calculation

Not applicable.

## 4 Change to protocol specified analyses

Not applicable.

## 5 Appendix

### 5.1 Imputation rules

#### 5.1.1 Study drug

Any partial dates or gaps between dates should be resolved. The end date of study drug is derived by using the last non-zero dose end date from the dose administration record CRF page.

If after DBL the partial dates still exist for end date, the imputation rule is as below:

If Month and Year is present, but day is missing, set the end date to be the first day of the month. If after imputation of day, study medication end date is earlier than study medication start date set study medication end date to study medication start date.

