#### **2.4.1 Study treatment / compliance**

**Duration of exposure in treatment period 1** is considered by taking into account the duration of exposure to ruxolitinib or placebo.

Duration of exposure in treatment period 1 (days) = (date of last administration of study treatment in treatment period 1) – (date of first administration of study treatment in treatment period 1) + 1.

**Duration of exposure in treatment period 2** is considered by taking into account the duration of exposure to open label ruxolitinib.

Duration of exposure in treatment period 2 (days) = (date of last administration of study treatment in treatment period 2) – (date of first administration of study treatment in treatment period 2) + 1.

Summary of duration of exposure in treatment period 1 of study treatment in appropriate time units will include categorical summaries and continuous summaries (i.e. mean, standard deviation etc) using appropriate units of time.

**Duration of follow up** is defined as last contact date – randomization date + 1.

The **average daily dose** refers to the actual daily dose administered.

The **cumulative dose in treatment period 1** refers to the total actual dose administered, over the duration exposure in treatment period 1.

**Dose intensity in treatment period 1 (DI1)** for subjects with non-zero duration of exposure in treatment period 1 is defined as follows:

$DI1 \text{ (mg/day)} = \text{Actual Cumulative dose in treatment period 1 (mg)} / \text{Duration of exposure to study treatment in treatment period 1 (days)}$ .

The number of subjects who have dose reductions, permanent discontinuations or interruptions, and the reasons, will be summarized separately for each of the study treatment components.

‘Dose changed’, ‘Dose interrupted’, and ‘Dose permanently discontinued’ fields from the Dosage Administration CRF pages (DAR) will be used to determine the dose reductions, dose interruptions, and permanent discontinuations, respectively.

The corresponding fields ‘Reason for dose change/dose interrupted’ and ‘Reason for permanent discontinuation’ will be used to summarize the reasons.

For the purpose of summarizing interruptions and reasons, in case multiple entries for interruption that are entered on consecutive days with different reasons will be counted as

separate interruptions. However, if the reason is the same in this block of entries, then it will be counted as one interruption.

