## 2.8 Safety analyses

For all safety analyses, the safety set will be used. All listings and tables will be presented by treatment group.

The overall observation period will be divided into four mutually exclusive segments:

**pre-treatment period:** from day of patient's informed consent (molecular pre-screen or main study informed consent) to the day before the first administration of study treatment

**on-treatment period 1:** from day of start of study treatment to minimum of (1) 30 days following the last date of study treatment in period 1 and (2) start of open label ruxolitinib in treatment period 2:

[Start date of study treatment; min(last date of study treatment in treatment period 1 + 30 days, start date of open label ruxolitinib in treatment period 2 – 1 day)].

**on-treatment period 2:** from start day of open label ruxolitinib to 30 days following the last date of study treatment in period 2:

[Start date of open label ruxolitinib in treatment period 2; last date of open label ruxolitinib in treatment period 2 + 30 days].

**post-treatment period:** starting at day 31 after last dose of study treatment.

On-treatment assessment is defined as any assessment reported in the on-treatment period 1 or 2.

Safety summaries (tables, figures) include data from the pre-treatment period (to display the baseline status) and the on-treatment period 1. Data from the on-treatment period 2 (if provided) and the post-treatment period (if provided) with the exception of deaths should not be included.

In particular, summary tables for adverse events (AEs) will summarize only on-treatment events, with a start date during the on-treatment period 1, the so-called *treatment-emergent* AEs for period 1.

However, all safety data (including those from the post-treatment period if provided) will be listed and those collected during the pre-treatment, treatment period 2 and post-treatment period will be flagged.

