#### 5.1.2 AE date imputation

Summary tables for adverse events (AEs) have to include only AEs that started or worsened during the on-treatment period, the *treatment-emergent* AEs. However, all safety data (including those from the post-treatment period) will be listed and those collected during the pre-treatment and after 30 days of post-treatment period are to be flagged.

Any missing onset date, causality, or severity must be queried for resolution. Unsolved missing values will be imputed according to the following:

- An unsolved missing causality will be left as missing.
- An unsolved missing severity will be left as missing in the AE tables. For AEs listed by highest severity, AE terms with missing severity will be excluded.
- An unsolved missing onset date will be imputed by the date of **Day 2**, which will force the AE to be treatment emergent, with the following exceptions:
  - If the stop/resolution date is prior to Study Day 1, the AE will then be considered as not being treatment-emergent.

- If both the month and day of the onset date are missing, and the last day of the year is prior to Study Day 1, the AE will then be considered as not being treatment-emergent.
- If only the day of the onset date is missing, and the last day of the month is prior to Study Day 1, then the AE will be considered as not being treatment-emergent.
- If only the day of the onset date is missing, and the 1st day of the month is after Study Day 1, the AE will then be considered as being treatment-emergent, and the incomplete date will be imputed as the 1st of the month.
- If the non-missing stop/resolution date is equal to Study Day 1, the AE will then be considered as not being treatment-emergent.

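### A last-dose date with its day still missing after database lock is set to the first of the month, which can only shorten exposure and can move late adverse events and laboratory values out of the on-treatment summaries

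*SAP*

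**What the plan says.** SAP 5.1.1 opens with a data-cleaning instruction: "Any partial dates or gaps between dates should be resolved". The imputation is a fallback, introduced by "If after DBL the partial dates still exist for end date, the imputation rule is as below". If the month and year are known and the day is not, the instruction is to "set the end date to be the first day of the month". There is one safeguard: if the result falls before the start date, "set study medication end date to study medication start date".

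The imputed date is then used in several places:

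- **Exposure (SAP 2.4.1).** Duration in Treatment Period 1 is last administration minus first administration plus 1. It is also the denominator of dose intensity.
- **On-treatment window (SAP 2.8).** On-treatment period 1 runs to the earlier of "30 days following the last date of study treatment in period 1" and the day before open-label ruxolitinib starts. Adverse event summaries count only events that start in that period. Other events are listed and flagged.
- **Laboratory summaries (SAP 2.8.3).** Values are included up to 30 days after the last administration.
- **Deaths (SAP 2.8.2).** On-treatment deaths and all deaths are summarised separately.

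For an adverse event with an unresolved onset date, SAP 5.1.2 works in the other direction. Its default is Day 2, "which will force the AE to be treatment emergent", with listed exceptions.

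**The concern.** The first of the month is the earliest date the record allows, so the error has one sign. The last dose is never placed too late and, unless the patient really stopped on the 1st or the start-date floor happens to give the true date, it is placed too early. The end of the safety window is tied to that date and can move earlier with it.

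Two things make the direction matter. First, the SAP resolves doubt about adverse event onset by default in favour of counting the event, but resolves doubt about the end of the same window by closing it sooner. Second, Protocol 6.3.2 requires adverse event follow-up for 30 days after the last dose, and Protocol 6.3.1.3 notes that myelofibrosis symptoms may return about a week after stopping. The interval at risk of being cut off is thus one that the protocol chose to observe. The trial was terminated early and is reported descriptively with few patients (SAP 1 and 1.2), so one reclassified event can visibly change a percentage.

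**Working it through.** The plan gives no figure to reproduce. The check is calendar arithmetic with the SAP's own definitions.

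**Size of the shift.** Shortfall = true day of month − 1.

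- 31-day month: maximum 31 − 1 = 30 days, mean 15.0
- 30-day month: maximum 29, mean 14.5
- February: maximum 27 or 28, mean 13.5 or 14.0
- All 731 days of 2016 and 2017, stop day uniform (assumption): mean 10,774 / 731 = 14.7 days

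The shortfall is never negative.

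**Worked case (assumed dates).** First dose 10 January 2017, true last dose 31 March 2017, recorded only as March 2017, no entry into Period 2.

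| Last dose used | Exposure (last − first + 1) | Window end (last + 30 days) |
|---|---|---|
| True, 31 March | 22 + 28 + 31 = 81 days | 30 April |
| SAP rule, 1 March | 22 + 28 + 1 = 51 days | 31 March |

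Adverse events starting from 1 to 30 April leave the treatment-emergent tables. Laboratory values from those days leave the laboratory summaries.

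**Which events can be lost.** Only those starting between the imputed date + 31 days and the true last dose + 30 days. The 1st of a month + 30 days is the 31st in a 31-day month and falls in the next month otherwise. Every true dosing day therefore lies inside the imputed window, and what can be lost starts after the true last dose.

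**Effect of the Period 2 limit.** The window ends at min(last dose + 30, Period 2 start − 1). With the same true last dose of 31 March:

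| Period 2 starts | True window end | Window end under SAP rule | Days lost |
|---|---|---|---|
| 1 day later | 31 March | 31 March | 0 |
| 7 days later | 6 April | 31 March | 6 |
| 14 days later | 13 April | 31 March | 13 |
| 31 days later | 30 April | 31 March | 30 |

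The exposure loss for Period 1 is still 30 days in each row.

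**Effect of the start-date floor.** With first dose 20 March and true last dose 31 March, the imputed date is 20 March. The shortfall is 11 days, and exposure falls from 12 days to 1. The floor is loosely worded. SAP 2.1.2 uses the start date of study treatment for the first non-zero dose. If that is the meaning here, a last dose record that starts on 15 June and ends on an unknown day in June would be closed on 1 June, before it began. The text does not exclude this.

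**The case against.** The strongest reply is that the rule may never be used. Partial dates are to be resolved first, and there is material to resolve them with: dosage administration records, discontinuation registered in the IRT (Protocol 7.1.5), data queries (Protocol 9.4), and a discontinuation date on the End of Treatment eCRF (SAP 2.1.9). The documents give no count of affected patients. This stands, and it is why the point ranks low.

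It can also be said that the choice of anchor is a trade-off. The first of the month never overstates exposure, and the rule is the same in both arms. That is true, but exposure and the safety window carry different risks. For safety tabulation, leaving out a doubtful event is the less cautious error, and the SAP's own onset rule takes the other side.

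A reader might infer stronger things that the documents do not support:

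- **That deaths disappear from the tables.** SAP 2.8 exempts deaths from the exclusion of post-treatment data, and SAP 2.8.1 and 2.8.2 tabulate all deaths. Only the on-treatment label can change.
- **That the events are lost from the report.** SAP 2.8 lists all safety data, with post-treatment data flagged.
- **That events during dosing are lost.** The calculation shows they are not.
- **That every affected patient loses the same number of days of follow-up.** The Period 2 limit and the start-date floor reduce the loss, in some cases to nothing.

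**Conclusion.** The point holds as a minor one. For a last-dose date still missing its day after lock, the rule errs only towards an earlier stop: by up to 30 days, and by about 15 on average if stop days are uniform over the month, which the documents neither state nor contradict. Exposure is understated by that amount. Adverse events and laboratory values from the tail of the true 30-day follow-up can leave the summaries while remaining listed and flagged. A death can change from on-treatment to post-treatment but stays in the all-deaths table.

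The effect depends on at least one partial date surviving lock, on the patient not moving promptly into Period 2, and on something having happened in the lost interval. No conclusion in the plan is shown to depend on it. The reason to act is that the direction is wrong for safety reporting and out of line with SAP 5.1.2, and the correction is cheap.

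**What to change.** Replace the rule in SAP 5.1.1. If only the day is missing, impute the last day of the known month, then cap it at the earliest of:

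- the discontinuation date on the End of Treatment eCRF;
- the date of death;
- for Treatment Period 1 dates, the start of Period 2 minus 1 day;
- the data cut-off date.

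Do not let the result fall before the start of the last recorded non-zero dose record. This also settles which start date the floor refers to.

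In the worked case this gives 31 March, 81 days of exposure and a window to 30 April, all equal to the truth. Provided the capping dates are themselves correct, the true window is never shortened.

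The cost is a short SAP edit and an error that now runs the other way. Before the caps apply, exposure and the window can be overstated by up to 30 days: had the true last dose been 1 March, 81 days would be reported instead of 51. A few post-treatment events may then be counted as treatment-emergent. That is the conservative direction for safety and agrees with SAP 5.1.2. The report should state how many last-dose dates were imputed, so that a reader can see whether the rule mattered.

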#### 5.1.2 AE date imputation

Summary tables for adverse events (AEs) have to include only AEs that started or worsened during the on-treatment period, the *treatment-emergent* AEs. However, all safety data (including those from the post-treatment period) will be listed and those collected during the pre-treatment and after 30 days of post-treatment period are to be flagged.

Any missing onset date, causality, or severity must be queried for resolution. Unsolved missing values will be imputed according to the following:

- An unsolved missing causality will be left as missing.
- An unsolved missing severity will be left as missing in the AE tables. For AEs listed by highest severity, AE terms with missing severity will be excluded.
- An unsolved missing onset date will be imputed by the date of **Day 2**, which will force the AE to be treatment emergent, with the following exceptions:
  - If the stop/resolution date is prior to Study Day 1, the AE will then be considered as not being treatment-emergent.

- If both the month and day of the onset date are missing, and the last day of the year is prior to Study Day 1, the AE will then be considered as not being treatment-emergent.
- If only the day of the onset date is missing, and the last day of the month is prior to Study Day 1, then the AE will be considered as not being treatment-emergent.
- If only the day of the onset date is missing, and the 1st day of the month is after Study Day 1, the AE will then be considered as being treatment-emergent, and the incomplete date will be imputed as the 1st of the month.
- If the non-missing stop/resolution date is equal to Study Day 1, the AE will then be considered as not being treatment-emergent.

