### 2.1.7 Study day

The term assessment will be used to represent an evaluation, a measurement or an event (e.g. AE onset, laboratory abnormality occurrence, disease progression, etc)

The study day *for efficacy assessments* will be calculated as follows:

Study day = date of assessment – randomization date + 1  
*if date of assessment is after the randomization date.*

Study day = date of assessment – randomization date  
*if date of assessment is before the randomization date.*

The study day *for safety assessments* will be calculated as follows:

Study day = date of assessment – start date of study treatment + 1  
*if date of assessment is after the randomization date.*

Study day = date of assessment – start date of study treatment  
*if date of assessment is before the randomization date.*

For any assessment or events such as baseline disease characteristics or medical history (e.g., time since diagnosis of disease) that is supposed to occur prior to randomization/start date of the study treatment, study day will be negative. There is no Day 0 defined.

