### 5.1.3.2 Post therapies date imputation

#### Start date:

- If Day is missing, then impute to the max (reference start date, first day of the month).
- Day and month are missing then impute to the max(reference start date, Jan 1)
- Reference start date will be last date of study treatment administration + 1.

End date: No imputation

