### 5.1.3.3 Other imputations

#### Missing death date

For cases when either day is missing or both month and day are missing for the date of death, the following imputation rules will be implemented:

- If only day is missing, then impute max [(1 mmm-yyyy), min(last contact date+1 , cutoff date)].

If both day and month are missing, then impute max [(1 Jan-yyyy, min (last contact date +1, cutoff date)].

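### SAP 5.1.2 dates an adverse event to Day 2 when its onset is known only to fall in a year after the year of Day 1; the study-day formulas in SAP 2.1.7 need a secondary wording correction

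*SAP*

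**What the plan says.** **AE onset (SAP 5.1.2).** A missing onset must be queried. If it stays unresolved it is dated Day 2, "which will force the AE to be treatment emergent, with the following exceptions". The five exceptions are:

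1. The stop date is before Day 1: not treatment-emergent.
2. "both the month and day of the onset date are missing, and the last day of the year is prior to Study Day 1": not treatment-emergent.
3. The month is known and ended before Day 1: not treatment-emergent.
4. The month is known and began after Day 1: "the AE will then be considered as being treatment-emergent, and the incomplete date will be imputed as the" first of that month.
5. The stop date equals Day 1: not treatment-emergent.

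**Use of the onset date (SAP 2.8).** AE summary tables take only events "with a start date during the on-treatment period 1". That period ends at the earlier of "last date of study treatment in treatment period 1 + 30 days" and the day before open-label ruxolitinib starts. Events in Period 2 or post-treatment are listed and flagged but not tabulated, apart from deaths.

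**Study day (SAP 2.1.7).** Efficacy days count from randomisation and safety days from the start of study treatment. In both formulas the +1 branch applies "if date of assessment is after the randomization date", and the other branch applies to dates before randomisation. The section rules out a Day 0.

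**The concern.** The exceptions in SAP 5.1.2 cover a recorded year that is over before Day 1, but not a recorded year that begins after it. Such an onset goes to Day 2, a date the record excludes. A more complete record is treated better: January 2017 becomes 1 January 2017, while 2017 alone goes back to Day 2.

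Day 2 always lies in on-treatment period 1. An event that the record places after Period 1, for instance on open-label ruxolitinib, would therefore be counted under the patient's blinded arm, which may be placebo. SAP Table 1-1 names AE duration among the endpoints of interest. SAP 2.8.1 specifies no duration table, but any duration computed from the Day 2 date would be too long by the same number of days.

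The study-day slip is a separate and lesser matter. The safety formula counts from one date and branches on another.

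**Working it through.** There is no stated figure to reproduce; this is date logic. The calendar dates below are illustrative, because the documents give no patient dates.

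**1. Does any exception catch a later year with no month?**
- Exceptions 3 and 4 need a known month, so they do not apply.
- Exceptions 1 and 5 need a stop on or before Day 1, which is impossible for an event starting in a later year.
- Exception 2 needs the year to end before Day 1, so it does not apply.
- Result: the Day 2 default applies. Coding the rule literally for every Day 1 in a 366-day year, with onset recorded only as the next year, gave the default in all 366 cases. In 365 of them the imputed date lay outside the recorded year. The exception is Day 1 on 31 December, where Day 2 is 1 January.

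**2. Smallest possible error** = 1 January of the recorded year minus the Day 2 date.
- Day 1 on 15 Oct 2016, onset 2017: the imputed date is 16 Oct 2016. There are 15 days to 31 Oct, 30 in November, 31 in December and 1 to 1 January: 15 + 30 + 31 + 1 = 77 days.
- Day 1 on 1 Mar 2016, onset 2017: the imputed date is 2 Mar 2016, 305 days before 1 Jan 2017.

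The largest error is open. SAP 2.1 excludes events starting after the cut-off, and the cut-off date is not given.

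**3. When is the event certainly in the wrong period?** Take an onset year one later than the year of Day 1. Period 1 is over by 31 December if the last blinded dose was on or before 1 December (1 Dec + 30 days = 31 Dec), or if open-label ruxolitinib began on or before 1 January. Example: Day 1 on 1 Mar 2016 and last blinded dose on 31 Aug 2016. The window closes no later than 31 Aug + 30 days = 30 Sep 2016, yet an onset recorded as 2017 is tabulated in Period 1.

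**4. The later-month rule.** The imputed date is the first of the recorded month. SAP 2.8 sorts events by start date and counts Period 2 as on-treatment. A date in Period 2 is therefore treatment-emergent and stays out of the Period 1 tables. Only a date after the on-treatment period conflicts: SAP 5.1.2 calls the event treatment-emergent, while SAP 2.8 places it post-treatment.

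**5. Safety study day.** Let r be the randomisation date and r + d the first dose. For a date r + j with j > 0, the literal formula gives j − d + 1.

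| d | r | r+1 | r+2 | r+3 |
|---|---|---|---|---|
| 0 | none | 2 | 3 | 4 |
| 1 | none | 1 | 2 | 3 |
| 2 | none | **0** (should be −1) | 1 | 2 |
| 3 | none | −1 (should be −2) | **0** (should be −1) | 1 |

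A delay of 0 or 1 day gives no Day 0. A delay of 2 or more gives one Day 0 and d − 1 labels that are one too high. The randomisation date meets neither branch at any delay, in the efficacy formula as well.

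**The case against.** The strongest reply is that the case is very unlikely. AEs are collected at every visit, 4 to 12 weeks apart, and missing onsets must be queried. A record left with a later year and no month needs several failures, and its true onset must also fall after Period 1 before any table is wrong. The report is descriptive. All of that stands and limits the point to a minor one. It could also be said that the default is meant for wholly missing dates. That does not hold, because exceptions 2 to 4 are for partial dates. On that reading the case would simply have no rule.

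Four stronger readings are tempting, and the documents do not support them.

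- A reader might infer that the later-month rule conflicts with SAP 2.8 whenever Period 1 has ended. It does so only for post-treatment dates, as step 4 shows.
- A reader might infer that SAP 5.1.2 alone departs from a convention of keeping the recorded year. The post-therapy start rule (5.1.3.2) and the death-date rule (5.1.3.3) never impute before 1 January of that year. But the concomitant-medication rule (5.1.3) has the same omission. The prior-therapy rule (5.1.3.1) can also leave the recorded year: with treatment start on 3 January, the seven-day limit moves an end date to 27 December of the year before. The point rests on the contradiction with the record, not on a consistent convention.
- A reader might let onset run to 31 December 2017 and quote errors above a year. That ignores the cut-off. If the cut-off were near the SAP amendment date of 19 July 2017 (an assumption), the 15 October example would span 77 to 77 + 199 = 276 days.
- A reader might infer that the study-day slip changes results. Baseline (SAP 2.1.8) and treatment emergence (SAP 2.8) are set by dates, and the baseline window in SAP Table 2-2, Days −40 to 1, absorbs the one-day shift. The intent is also clear from the exclusion of Day 0 and from the footnote to SAP Table 2-1.

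**Conclusion.** SAP 5.1.2 is wrong as written for one case: an unresolved onset known only to be in a year after the year of Day 1. The Day 2 date contradicts the record for every Day 1 except 31 December with onset in the next year. It places the event in the Period 1 tables whether or not Period 1 had ended. In the worked example the date is at least 77 days too early, and the upper limit cannot be stated without the cut-off date.

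For the later-month rule, the need is a clarification for post-treatment dates. The study-day formulas in SAP 2.1.7 contain a real slip, but it affects labels only. Day 0 needs a first dose two or more days after randomisation, whereas the protocol plans both for Day 1.

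The conclusion about the text needs no assumption beyond a literal reading. The practical effect is judged small because the rule acts only after failed queries and the report is descriptive. The number of affected records is not given. This is a minor correction, worth making because it costs almost nothing.

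**What to change.** **SAP 5.1.2**
- Add a rule: if only the onset year is known and it is later than the year of Day 1, impute 1 January of that year, in parallel with the existing later-month rule. Assign the treatment period from the imputed date under SAP 2.8. Keep Day 2 when the recorded year is the year of Day 1.
- If Period 1 ended during the recorded year, keep the event in Period 1 and flag its period as uncertain in the listing.
- For the later-month rule, state that the imputed date decides the period under SAP 2.8, so that an onset after the on-treatment period is not called treatment-emergent.

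**SAP 2.1.7**
- Branch the safety formula on the treatment start date and the efficacy formula on the randomisation date. In each, use on or after (with +1) and before (without). The day before first dose is then −1, the day of first dose is 1, and the randomisation date always has a value.

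**Cost.** A few lines of SAP wording and programming. The new year rule cannot remove a true Period 1 event, because 1 January is the earliest onset the record allows: if that date is after Period 1, so is every possible onset. What remains is that the imputed onset may still be up to 364 days early in a 365-day year (less if the cut-off falls within it), and that events of uncertain period stay in Period 1 with a flag. The study-day correction has no analysis cost.
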